#### Visit 14: Concluding visit

This visit will take place at least 30 days after V13, approximately 120 weeks after first administration (V1) with a permitted deviation of up to 14 days, or in case of recurrence or early withdrawal.

The following procedures will be performed:

- Recording of concomitant medication
- Recording of (serious) adverse events and potential Immune-Mediated Diseases
- Routine physical examination including WHO performance status assessment
- Cross-sectional imaging or Magnetic Resonance Imaging (CT scan or MRI of chest, abdomen and pelvis)
- Pregnancy test

A pregnancy test will be repeated every 3 months for females of childbearing potential and should be performed at any time during the study for all women of childbearing potential if the investigator or patient suspects that pregnancy has occurred while the subject was being treated on protocol therapy.

- Blood sampling for safety

Note that as of Protocol Amendment 4.0, Smoking status and blood sampling for immunological examination (optional, if patient specifically consents to this), as mentioned in the original protocol, will not be performed anymore.

As of Protocol Amendment 4.0 the follow-up visits have been cancelled.

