## 7. STUDY ASSESSMENTS AND PROCEDURES

### 7.1 General Study Aspects

#### Attendance for study visits

It is the investigator's responsibility to ensure that the intervals between visits/contacts are strictly followed.

Patients will be required to attend for study treatment administration and assessment according to the schedule shown below (Section 7.2). The first study treatment will take place maximum 7 days after randomization. Permitted deviation from the stipulated date of each visit (due e.g. to weekends or public holidays) will be as follows:

Screening 1:	prior to or shortly after cystectomy
Screening 2:	
For patients not receiving adjuvant chemotherapy	max 13 weeks after cystectomy
For patients receiving adjuvant chemotherapy	within 3-6 weeks after the last day of chemotherapy administration
Visit 1:	max 7 days after randomization and max 36 weeks after cystectomy
Visits 2-5:	± 4 calendar days.
Visits 6-13:	± 14 calendar days.

The concluding visit will take place at least 30 days after the patient's last dose of study product.

The follow-up visits planned in the initial study protocol has been cancelled.

Any deviation greater than this will be regarded as a protocol violation.

In each case, the sponsor will decide, if appropriate in consultation with the IDMC, whether the violation is to be regarded as:

- A minor violation (i.e., without consequence),
- A major violation (resulting in exclusion of the patient from the population of patients evaluable according to protocol (ATP)).

When the permitted deviations are applied or when a study treatment has to be postponed (refer to Section 6.3.2.1 for details on postponement of study treatment), the next study visit should be planned at a time allowing:

- A minimum of 14 days between 2 treatment administrations,
- To keep up with the schedule as based on the date of first study treatment administration (Visit 1).

*During the treatment phase, 1 week equals 7 calendar days. During the treatment phase timings will be counted in weeks.*

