study will continue only with patients from the active treatment group who will decide to stay in the study. Signature of the ICF addendum will be documented in eCRF at visit S2.

These visits will take place at 12-weekly intervals i.e. at time points 24, 36, ...108 weeks after V1, with a permitted deviation of up to 14 days.

During Visit 6 to Visit 13 the following procedures will be performed:

- Recording of concomitant medication (each visit)
- Recording of (serious) adverse events and potential Immune-Mediated Diseases (each visit)
- Routine physical examination including WHO performance status assessment (each visit)
- Cross-sectional imaging or Magnetic Resonance Imaging (CT scan or MRI of chest, abdomen and pelvis) (each visit)
- Pregnancy test (each visit)

A pregnancy test will be repeated every 3 months for females of childbearing potential and should be performed at any time during the study for all women of childbearing potential if the investigator or patient suspects that pregnancy has occurred while the subject was being treated on protocol therapy.

- Blood sampling for safety at V8, and V12

Note that as of Protocol Amendment 4.0, Smoking status (V6, V8, V10, V12), blood sampling for immunological examination (at V7, V8 and V10) and urine sampling (at the time of recurrence of bladder cancer in the urinary urothelium, for analysis of MAGE A3 expression, optional, if patient specifically consents to this), as mentioned in the original protocol, will not be performed anymore.

Before each administration the criteria for permanent stopping or postponement of study treatment (Sections 6.3.2.1 and 6.3.2.2) will be checked. If any of these is met, the patient will be withdrawn from study treatment or the administration of study treatment will be postponed.

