## Reporting of pIMDs

The standard time period for collecting and recording of pIMDs will begin at the first receipt of study medication and will end at the concluding visit.

Once onset of any new pIMD or exacerbation of a pre-existing pIMD is diagnosed (serious or non-serious) in a study patient, the investigator (or designate) must complete, date and sign an SAE Report Form and forward it to the Sponsor WITHIN 24 HOURS after he/she becomes aware of the diagnosis. A field on the SAE Report Form allows to specify that the event is a pIMD and whether it is serious or non serious. The SAE Report Form will always be completed as thoroughly as possible with all available details of the event, in accordance with the pIMD standard questionnaire provided. Even if the investigator does not have all information regarding a pIMD, the form should still be completed and forwarded to the Sponsor within 24 hours. Once additional relevant information is received, the form should be updated and forwarded to the Sponsor WITHIN 24 HOURS.

The investigator will always provide an assessment of causality at the time of the initial report.

Fax transmission or a scanned report per e-mail are the preferred methods to forward the SAE Report Form to the Study Contact for Reporting SAEs. In absence/dysfunction of fax/e-mail equipment, the Study Contact for Reporting SAEs must be notified by telephone within 24 hours. As soon as the fax/e-mail equipment is working again, the investigator (or designate) must fax/e-mail the SAE Report Form to the Study Contact for Reporting SAEs within 24 hours.

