## **8.6 Detecting and recording adverse events, serious adverse events**

### **Time Period, Frequency, and Method of Detecting Adverse Events and Serious Adverse Events**

All non-serious AEs occurring within the period beginning at the first administration of study treatment and ending 30 days after the last administration of study treatment must be recorded on the Adverse Event form in the patient's eCRF, irrespective of intensity or whether or not they are considered study treatment-related.

All SAEs must be recorded from the first administration of study treatment till the concluding visit (Visit 14, Week 112 or later) and at least 30 days after the last administration of study treatment in the event of early discontinuation of study treatment administration.

Additionally, in order to fulfil international reporting obligations, SAEs that are related to study procedures will be reported from the date of signature of informed consent. However, cystectomy before the first administration of study treatment is not considered as a study procedure. Therefore, foreseeable AEs and SAEs specifically related to the cystectomy prior to first study treatment administration should not be reported. See Section 8.9 for instructions for reporting and recording SAEs.

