## 9. PATIENT COMPLETION AND WITHDRAWAL

### 9.1 Patient Completion

A patient will be considered to have completed the study treatment when he/she has been under treatment till Week 112 (= the end of all the scheduled study visits defined as the concluding visit) following first study treatment administration. The term “study activity” refers to physical visits and does not include follow-up contacts (i.e. phone contacts).

Treatment with investigational treatment (ASCI or placebo) should be conducted and completed according to this protocol unless it has to be ended prematurely because of documented disease recurrence, withdrawal due to an unacceptable toxicity, or withdrawal for other reasons (see Section 9.2).

Once the patient has been withdrawn from investigational treatment or has completed treatment, the reason for cessation of treatment must be documented in the patient’s medical records and eCRF.

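### Visit 14 is at week 112 in some sections and about week 120 in another, so SAE and pIMD collection after the last dose can run for 30 days or for about 84

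*Combined protocol and SAP*

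**What the plan says.** The last planned dose is given at Visit 13. Section 7.3.2 spaces Visits 6 to 13 twelve weeks apart, with the last of them at week 108 from first dose, and lets each move by as much as two weeks. Table 5 agrees and puts Visit 13 at week 108.

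The timing of Visit 14 is given differently in different places:

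- Table 5: week 112.
- Section 9.1: a patient has completed treatment after being "under treatment till Week 112 (= the end of all the scheduled study visits defined as the concluding visit) following first study treatment administration".
- Section 8.6: SAEs are recorded "till the concluding visit (Visit 14, Week 112 or later").
- Section 10.3: the yearly safety analysis runs until Visit 14, which is put at 112 weeks after the last patient's randomization.
- Section 7.3.2, Visit 14: "approximately 120 weeks after first administration (V1) with a permitted deviation of up to 14 days". The same sentence sets a minimum of 30 days after Visit 13.

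The minimum gap is also in Section 7.1: "The concluding visit will take place at least 30 days after the patient's last dose of study product". The synopsis (Timing) and Section 4 repeat it.

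Two safety collection periods end at this visit. Under Section 8.3 the pIMD period "will begin at the first receipt of study medication and will end at the concluding visit". Under Section 8.6 the SAE period also runs from first dose to the concluding visit, with a 30-day minimum after the last dose if treatment stops early. Non-serious adverse events are different: their period ends a fixed 30 days after the last dose, whenever Visit 14 takes place.

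**The concern.** All of these statements are current text, and they cannot all hold. Week 112 and week 120 are eight weeks apart, and week 112 counted from week 108 appears to breach the 30-day minimum.

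This is more than clerical because Visit 14 closes SAE and pIMD collection for patients who finish dosing. Nothing scheduled afterwards would recover a missed event: the follow-up visits are cancelled, and Section 8.11 does not oblige investigators to look for events once the detection period is over. It requires notification only of an SAE that the investigator happens to learn of and considers reasonably related to the product. A non-serious pIMD, or an SAE judged unrelated, that arises between the two possible visit dates is recorded at one site and lost at another.

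Section 10.3 tabulates adverse events per treatment group and names no common period after the last dose. The period need not be alike in the two arms either. Placebo patients still on treatment at Amendment 4.0 stop dosing before Visit 13 and have only the 30-day minimum to time their concluding visit, while active patients may go on to Visit 13.

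**Working it through.** **Inputs.** Five doses at 3-week intervals, then eight at 12-week intervals (Table 1, Section 7.3.2). One week is 7 calendar days in the treatment phase (Section 7.1). Minimum gap from last dose to Visit 14: 30 days (Section 7.1). Visit 14 at week 112 (Table 5, Section 9.1) or at week 120 ± 14 days (Section 7.3.2).

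**Step 1, reproduce Visit 13.** 4 × 3 + 8 × 12 = 12 + 96 = week 108. This matches the protocol and is day 756.

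**Step 2, earliest Visit 14 under the minimum.** 756 + 30 = day 786, and 786 / 7 = week 112.3. Week 112 is close to this but two days early. Week 120 does not come from the 30-day rule; it equals Visit 13 plus 12 weeks.

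**Step 3, days from last dose to Visit 14.**

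- Week 112: (112 − 108) × 7 = 28 days, which is 2 days short of 30.
- Week 120: (120 − 108) × 7 = 84 days; with ± 14 days, 70 to 98.

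**Step 4, does the deviation bridge the gap?** 120 weeks ± 14 days is week 118 to week 122. It does not reach week 112 or week 112.3.

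**Step 5, length of collection after the last dose.**

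- Nominal dates: 84 / 28 = 3.0.
- With the 30-day minimum observed: 84 / 30 = 2.8, with a range of 70 / 30 = 2.3 to 98 / 30 = 3.3.
- The stretch that may or may not be covered runs from day 30 to day 84, which is 54 days, or to day 98 at the latest.

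**Step 6, length of the whole collection period from first dose.**

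- Nominal dates: 120 / 112 = 1.07.
- With the minimum observed: 840 / 786 = 1.07.
- At the latest permitted date: 854 / 786 = 1.09.

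**Step 7, the anchor in Section 10.3.** First dose may follow randomization by up to 7 days (Section 7.1). So 112 weeks after randomization is week 111 to week 112 after first dose. This sentence dates the end of the yearly safety analysis for the trial; it does not instruct a site when to hold the visit.

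**The case against.** The strongest reply is that the 30-day minimum settles the matter. It is stated four times, and week 112 is just 108 weeks plus 30 days rounded down. Section 8.6 makes week 112 a floor rather than a date, so for SAEs it is compatible with week 120. The minimum on the visit also sets a floor for SAE and pIMD collection, because both run until that visit. The analysis is descriptive, and no power or sample-size figure depends on Visit 14.

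Much of this stands. It disposes of three stronger conclusions that a reader might draw:

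- That the SAE and pIMD window differs threefold. Both windows start at first dose, so the whole differs by about 7%. The ratio of 3.0 concerns only the part after the last dose, and its 28-day denominator is ruled out by the minimum.
- That Visit 14 could fall 14 days after Visit 13, by taking 14 days off week 112. No section attaches that deviation to week 112, and the minimum bars such a gap.
- That the 30-day protection covers only non-serious events. The visit minimum is general, and Section 8.6 adds its own 30-day minimum for SAEs after early discontinuation.

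The affected group is also limited to patients who reach Visit 13. Treatment ends on 30 November 2016; 108 weeks (756 days) before that is 5 November 2014, so patients first dosed later than this cannot reach week 108 on schedule.

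The reply does not remove the contradiction. A minimum gives the earliest date and not the date, so a site may still hold the visit at day 30 or at day 84 and cite the protocol for either. The floor in Section 8.6 does not reconcile Table 5 and Section 9.1 with Section 7.3.2, and Section 8.3 gives pIMDs no end date apart from the visit itself.

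**Conclusion.** The point holds as an inconsistency with a real but bounded effect on safety capture. Visit 14 is at week 112 or about week 120 depending on the section, and nominal week 112 misses the protocol's own minimum by two days. For patients who reach Visit 13, collection of SAEs and pIMDs after the last dose can last 30 days or about 84 days, roughly 2.8-fold, and up to 98 days at the latest permitted date. Over the whole period from first dose the difference is about 7%.

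This assumes that Visit 13 is held on its nominal date and that sites observe the 30-day minimum. If Visit 13 moves within its 14 days, the gaps move with it. The documents do not say how many patients reach Visit 13 or which date sites used, so the number of events affected cannot be estimated. Table 9, which summarises the reporting periods, has no legible cell contents in the available text and is not relied on either way. The point deserves correction before the safety tables are produced; it does not call the design into question.

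**What to change.** Reconcile Table 5 and Sections 7.1, 7.3.2, 8.6, 9.1 and 10.3 to one timing for Visit 14, with one anchor, consistent with the stated 30-day minimum. Which timing is right is the sponsor's decision.

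In the descriptive safety analysis of Section 10.3, keep every collected SAE and pIMD in the main tables, so that late events stay visible. Add one summary per treatment group limited to a common period, from first dose to 30 days after last dose, which is the period the protocol already uses for non-serious adverse events. Flag events that occur after it. Identify patients whose collection ended before day 30: this can happen at recurrence, when Section 7.3.3 calls for the Visit 14 procedures before chemotherapy is given, and the added summary would not be complete for them.

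The cost is a text correction and one extra table. No data are discarded and no further visits are needed for the analysis change.

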### **7.3.3 Recurrence or progression**

All types of recurrence will be included i.e. local, regional and distant metastasis as well as second primary tumor of the upper urinary tract. In addition, all deaths occurring without prior documentation of tumor recurrence will be considered as an event. Any new primary cancer will not be considered as recurrence and should be reported as SAE.

All recurrences must be documented by radiological evidence or biopsy, as determined by the investigator.

[figure not shown]
Suspicion of relapse based on physical examination findings or laboratory signs must be confirmed by radiological examination and/or biopsy.

Equivocal findings on standard radiological imaging should be confirmed by repeated examinations or cytology/histology or other imaging techniques.

In the event of unequivocal, objective recurrence (at scheduled or unscheduled visit), the investigator will determine and record the recurrence, withdraw the patient from the study treatment

and perform all procedures as defined for Visit 14 before administration of chemotherapy to treat the recurrence. The investigator must inform the Sponsor as soon as possible.

The algorithm below summarizes how the date of recurrence should be determined.

Cxr, Chest X-Ray.

[figure not shown]
\* Date of imaging if equivocal, date of unplanned visit if symptoms present without imaging evidence.

\*\* CxR, CT scan/MRI, Bone scan, Biopsy of suspect lesion, etc.

\*\*\* Date of initial imaging (Day X) if equivocal, date of additional examinations (Day Z) if patient initially symptomatic without objective recurrence

[figure not shown]
**Scenario A:** As soon as a planned CT scan /MRI shows objective recurrence, the patient will be considered to have had a recurrence on the day of this planned imaging (Day X).

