### **3.3 Primary Endpoint**

Disease-free Survival (DFS):

- Defined as the time from randomization to either the date of first recurrence of the disease or the date of death (whatever the cause), whichever occurs first.
- Types of recurrence to be considered as an event include loco-regional and distant metastases.
- In addition, any death occurring without prior documentation of tumor recurrence will be considered as an event (and will not be censored in the statistical analysis) as this approach is less prone to introduce bias.

- If no event has occurred by the time of the analysis, then the time to event will be censored at the date of the last assessment of the patient in question.
- Any new primary cancer at another site, including transitional carcinoma of the upper urinary tract, will not be considered as recurrence and should be reported as a SAE.

As of Protocol Amendment 4.0, the primary endpoint will not be analysed as planned. All clinical data collected in the study will be analysed descriptively. See for rationale Section 2.6.2.

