Medical or scientific judgement should be exercised in deciding whether reporting is appropriate in other situations, such as important medical events that may not be immediately life-threatening or result in death or hospitalization but may jeopardize the patient or may require medical or surgical intervention to prevent one of the other outcomes listed in the above definition. These should also be considered serious. Examples of such events are second primary cancers, intensive treatment in an emergency room or at home for allergic bronchospasm, blood dyscrasias or convulsions that do not result in hospitalization.

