#### **8.4 Events or outcomes not qualifying as adverse events or serious adverse events / Progression / Recurrence of the Disease under study**

An event which is part of the natural course of the disease under study (i.e., disease progression, recurrence) is captured as an efficacy measure; therefore it does not need to be reported as a SAE.

Progression/recurrence of the tumor will be recorded in the clinical assessments in the eCRF. Death due to a progressive disease is to be recorded on a specific form in the eCRF but not as a SAE.

However, if the progression of the underlying disease is greater than that which would normally be expected for the patient, or if the investigator considers that there was a causal relationship between treatment with recMAGE-A3 +AS15 or protocol design/procedures and the disease progression/recurrence, then this must be reported as a SAE.

Any new cancer (non-related to the cancer under study) must be reported as an SAE.

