## **10. STATISTICAL CONSIDERATIONS**

### **10.1 Sample Size Calculation**

The assumptions for the sample size calculations were the following.

- Primary endpoint on which sample size is based is disease free survival (see Section 3.3)
- Hazard ratio of expected disease free survival of recMAGE-A3 + AS 15 ASCI treated patients relative to placebo treated patients that will be significant at the end of study is 0,75.
- Median Disease-Free Survival in the placebo groups is 24 months
- Recruitment period is 4-5 years
- All patients will be observed for a maximum of 5 years from their first study administration and with a minimum of 6 months after treatment completion.
- Null hypothesis H0: "there are no differences in expected disease free survival between the placebo treated patients and recMAGE-A3 + AS 15 ASCI treated patients.
- Alternative hypothesis H1: "the recMAGE-A3 + AS 15 ASCI treated patients have a different disease free survival compared to the placebo treated patients.
- Anticipated drop out percentage is 15 %
- One-sided alpha for final analysis is 0,05
- Power to detect a  $HR = 0,75$  is 50 %. Power to detect a  $HR = 0,65$  is 80 %.
- Randomization: 2 recMAGE-A3 + AS 15 ASCI patients versus 1 Placebo patient.
- Interim analysis planned when 65% of the total number of events have occurred.
- Calculations were done using East 5.3.

Based on these assumptions and in order to reach 155 events\* (see section 10.2), we needed a total of 273 patients for randomization. A total of 182 patients were to be randomized for treatment with recMAGE-A3 + AS 15 ASCI and 91 patients were to be randomized for treatment with placebo. Total number of evaluable patients (15 % drop out percentage) would be 231.

The power to detect a  $HR = 0,75$  (from 24 to 32 months) was 50%. The study would have 65% power if the true  $HR = 0,7$  (from 24 to 34 months) and 80% power if the true  $HR = 0,65$  (from 24 to 37 months).

Due to the Protocol Amendment 4.0, not all analyses described in this section will be performed and no interim analysis will be done. Please see Section 2.6.2 for the rationale.

\* 147 events without interim analysis

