### 10.3 Statistical Analyses

As of Protocol Amendment 4.0, statistical analyses will not be assessed as planned. All clinical data collected in the study will be analysed descriptively. Please see Section 2.6.2 for the rationale.

Patient characteristics, demographics and baseline measurements will be summarized in order to provide a characterization of the patient population. Descriptive statistics, e.g. mean, standard deviation, median, range, frequency distributions as appropriate will be presented for each randomization group: recMAGE-A3 + AS 15 ASCI versus the Placebo arm.

A yearly safety analysis will be performed until all patients have finished the treatment phase (Visit 14) which is 112 weeks after the last patient was randomized. The incidence and severity of all adverse events will be tabulated per treatment group. Treatment related toxicity > grade 2 will be descriptively described in both arms.

The description of the safety data will be performed, first globally then for each of the study arms. The safety analysis will be performed in all patients who are randomized and who received at least one Study Treatment Administration.

The efficacy analysis will be performed including all patients who are randomized and who received at least one Study Treatment Administration.

Disease free Survival (Section 3.3) will be estimated by means of the Kaplan Meier method and comparison between treatment groups will be done by means of the log-rank test.

A Cox proportional hazards model will be applied to correct for treatment effects and to assess the influence of prognostic and confounding factors such as T category, Neo-adjuvant Chemotherapy vs. Adjuvant Chemotherapy vs. no chemotherapy, N category, gender, centre, multifocality of bladder carcinoma (Y/N), age (continuous), presence of Carcinoma in Situ (CIS) and gene profile population.

The analyses of other outcome measurements will be analyzed in an exploratory way with methods appropriate for the type of the variable. Both the safety data and the efficacy data will be summarized by appropriate descriptive statistics.

For each patient entering, the reason for discontinuation (e.g. patient decision, urologists decision, lack of efficacy, adverse events) should be clarified. The description of the reason for discontinuation will be performed.

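### Section 7.3.3 counts an upper-urinary-tract second primary as a recurrence, while the DFS definition in Section 3.3 that the analysis cites excludes it.

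*Combined protocol and SAP*

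**What the plan says.** Section 3.3 counts loco-regional and distant recurrence, and death from any cause, as DFS events. It then rules out new primaries and names the upper tract: "Any new primary cancer at another site, including transitional carcinoma of the upper urinary tract, will not be considered as recurrence". The same bullet sends these tumours to SAE reporting.

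Section 7.3.3 tells the investigator how to establish, date and record a recurrence. It opens: "All types of recurrence will be included i.e. local, regional and distant metastasis as well as second primary tumor of the upper urinary tract". Two sentences later, in the same paragraph, it says: "Any new primary cancer will not be considered as recurrence and should be reported as SAE". That sentence makes no exception for the upper tract.

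The statistical sections refer only to Section 3.3. Section 10.1 has "Primary endpoint on which sample size is based is disease free survival (see Section 3.3" and Section 10.3 has "Disease free Survival (Section 3.3) will be estimated by means of the Kaplan Meier method".

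On safety reporting, Section 8.4 exempts recurrence: "An event which is part of the natural course of the disease under study (i.e., disease progression, recurrence) is captured as an efficacy measure", so no SAE report is needed for it. The same section adds: "Any new cancer (non-related to the cancer under study) must be reported as an SAE". Section 8.2, on important medical events that count as serious, says: "Examples of such events are second primary cancers".

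**The concern.** One clinical event receives opposite classifications in the endpoint definition and in the recording instruction. The investigator works from 7.3.3, and the analyst works from 3.3. If an upper-tract primary is entered as a recurrence, the data contain an event that the DFS definition excludes. DFSS inherits the problem because it also runs to first recurrence. Overall survival does not use recurrence and is unaffected.

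The SAE route is uncertain for the same reason. Called a recurrence, the tumour falls under the Section 8.4 exemption. Called a new primary, it must be reported. Two sites could treat identical cases differently, and the new-cancer SAE counts would reflect which sentence each site read. Safety monitoring continues during treatment under Amendment 4.0, so this part matters even though the efficacy analysis is now descriptive.

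The event is foreseeable. Baseline imaging is required to exclude upper-tract tumours, and CT or MRI of chest, abdomen and pelvis is scheduled at Visit 5, at Visits 6 to 13 and at the concluding visit.

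**Working it through.** **Comparing the texts.** For an upper-tract second primary in a patient with no earlier recurrence:

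| Source | DFS/DFSS recurrence? | SAE report? |
|---|---|---|
| 3.3 | No | Yes |
| 7.3.3, first sentence | Yes | Not needed, through the 8.4 exemption |
| 7.3.3, third sentence | No | Yes |
| 8.2 (second primaries) | not addressed | Yes |
| 8.4 (new cancer) | not addressed | Yes, if unrelated to the cancer under study |
| 10.1, 10.3 | As in 3.3 | not addressed |

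Only the first sentence of 7.3.3 makes the tumour a recurrence. No text states which rule prevails, but the sample size and the analysis both cite 3.3 and neither cites 7.3.3.

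**Size per affected patient.** Inputs: 83 randomized at the hold (Section 5.1) and 2:1 allocation (Section 4). An exact 2:1 split is assumed.

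- Overall: 1/83 = 1.2 percentage points.
- ASCI arm: 83 × 2/3 = 55.3 patients; 1/55.3 = 1.8 points.
- Placebo arm: 83 × 1/3 = 27.7 patients; 1/27.7 = 3.6 points.

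These are upper bounds on the change in the crude event proportion. Nothing changes if a true recurrence came first. Only the event date moves if a true recurrence or a death is observed later.

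**Planned design, for context.** The plan's event count reproduces. With one-sided alpha 0.05, 50% power, HR 0.75 and 2:1 allocation, the Schoenfeld formula gives (1.645 + 0)² / [(2/3)(1/3)(ln 0.75)²] = 2.706 / (0.2222 × 0.08276) = 147.1, against 147 stated without an interim analysis.

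The documents give no upper-tract rate. As an assumption only, let such tumours make up a share s of the placebo-arm event hazard and be unaffected by treatment. The HR then becomes (1 − s) × HR + s. At 155 events, ignoring the interim analysis, and a true HR of 0.65:

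- s = 0: HR 0.65, power 81%.
- s = 1% (roughly 2 events): HR 0.6535, power 80%.
- s = 5% (roughly 8 events): HR 0.6675, power 77%.

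The loss would have been modest even under the original plan. That test will not now be carried out as planned, so these figures do not decide the point.

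**The case against.** The strongest reply is that the third sentence of 7.3.3 already agrees with 3.3, so a careful site would classify the tumour correctly, and that no text says 3.3 prevails. The sponsor might have intended the reverse: Section 8.4 limits mandatory reporting to new cancers unrelated to the disease under study, and an upper-tract urothelial tumour is arguably related. The visit and assay sections also speak of recurrence in the urinary urothelium, which after cystectomy could include the upper tract.

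The ambiguity stands, but it does not remove the fault. A reader can take the specific inclusion as an exception to the general sentence that follows. The wording in 8.4 and on the urothelium is indirect, whereas 3.3 names the tumour and excludes it, and the statistical sections cite 3.3.

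The objections on weight are fair. No case is known to exist. The analysis is descriptive, recruitment has stopped and follow-up visits are cancelled. Section 9.2.1 gives a second tumour needing therapy as an example of another reason for stopping treatment, separate from recurrence, so some cases may already be identifiable. The crude proportion is also not the planned statistic. A Kaplan-Meier curve drops by its current value divided by the number at risk, which with censoring can exceed one over the number randomized. These points limit the consequence but leave the contradiction in place.

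**Conclusion.** The concern holds. The first sentence of 7.3.3 contradicts the DFS definition in 3.3 and the third sentence of its own paragraph, and 3.3 is the text the analysis relies on. Each affected patient moves the crude event proportion by at most 1.2 points overall, or about 1.8 points (ASCI) or 3.6 points (placebo) within an arm. These figures assume 83 patients split exactly 2:1. The denominator may differ slightly, because randomization of patients already consented or in screening was allowed until 3 February 2015 and the analysis uses treated patients. The number of cases is unknown and may be zero. What is at risk is the accuracy of the descriptive DFS and DFSS summaries and the consistency of new-cancer SAE counts. No efficacy decision depends on it. It should be fixed because it concerns what counts as a primary endpoint event and the correction is cheap.

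**What to change.** 1. In Section 7.3.3, delete the closing phrase of the first sentence that adds upper-tract second primaries. State there that such tumours are new primaries, reported as SAEs and not counted as DFS or DFSS events, as in Section 3.3.
2. Before the descriptive analysis, query every recorded recurrence for its site, using the pathology or radiology reports that Section 12.1 allows to be requested. The wording change alone does not correct entries already made.
3. Recode any upper-tract primary and confirm that an SAE report exists. A patient left without a DFS event is then censored at the last assessment, as Section 3.3 provides.
4. Optionally, show one sensitivity DFS estimate that counts these tumours as events.

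The cost is one protocol sentence, one data query and, if wanted, one extra estimate.
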